4.2.2. Feasibility

The ability of the baroloop Systems to be placed around a vagal nerve and the ability to stimulate at Day 14/21 post-implantation.

4.3. Secondary Study Endpoints

- The change in blood pressure recorded during intraoperative stimulation at the time of implantation.
- Mean reduction in 24-hour ambulatory systolic and diastolic blood pressure (ambulatory blood pressure monitoring - ABPM) at one (1), three (3), six (6), twelve (12), eighteen (18) and twenty-four (24) months post-treatment versus baseline.
- The composite MAE rate at 1, 3, 6, 12, 18 and 24 months post-procedure defined as:
 - All-causes of death
 - Hospitalization for hypertensive crisis post-titration
 - Any device or procedure-related serious adverse event
- The mean reduction in office diastolic and systolic blood pressure, and diastolic and systolic blood pressure at 1, 3, 6, 12, 18, and 24 months.
- Changes in antihypertensive medicines/doses through 1, 3, 6, 12, 18 and 24 months post-implantation as analyzed by Daily Defined Dosages (WHO Definition) and total medications.
- Quality of Life as measured by the Medical Outcomes Study 36-Item Short-Form Health Survey (SF-36).

4.4. Number of Subjects and Sites

Up to 10 subjects may be enrolled at up to 3 clinical study centers.

4.5. Study Population

The study population comprises subjects with resistant hypertension as defined in the 2018 ESC/ESH Guidelines for the management of arterial hypertension.

4.6. Enrollment Criteria

A potential subject must meet all of the criteria as outlined below in order to be considered eligible to participate in this study.

4.6.2. Exclusion Criteria

Potential subjects with one or more of the following criteria shall be excluded from the study even if they meet the inclusion criteria:

1. Any patient in whom access to the vagal nerve is limited by the size of the vagus (a size not compatible with the baroloop cuff).
2. Any patient with a history of injury to the vagus nerve or its branches (e.g., the recurrent laryngeal nerve).
3. Secondary causes of hypertension.
4. Calculated eGFR < 30 mL/min/1.73m².
5. Type 1 diabetes mellitus or poorly controlled type 2 diabetes mellitus (HbA1c > 10%).
6. One or more episodes of orthostatic hypotension in the past year
7. Requirement for chronic oxygen therapy or mechanical ventilation.
8. Untreated (no CPAP therapy) sleep apnea (AHI > 15)
9. Morbid obesity, defined as Body Mass Index >40 kg/m² or arm circumference 46 cm.
10. Pacemaker and/or implantable defibrillators.
11. History of transient ischemic accident or cerebrovascular accident during six (6) months prior to screening.
12. Symptomatic carotid artery disease or > 70% occlusion of either carotid artery; any carotid malformation or lesion, a carotid bruit or other abnormal carotid sound.
13. Prior surgery, radiation therapy or scarring in the neck in the region of the carotid artery (e.g., patients with a tracheostomy, extensive thymectomy or thyroid surgery).
14. Limited mobility of the neck secondary to vertebral disease or prior vertebral surgery, including patients who wear a cervical support.
15. History of heart failure (NYHA class III-IV or ejection fraction < 30%), myocardial infarction, unstable angina, coronary bypass or coronary angioplasty during six (6) months prior to screening.
16. Cardiac arrhythmias (atrial fibrillation, atrial flutter, etc.) that require anticoagulation or interfere with a consistent measurement of blood pressure.
17. Syncope in the last 6 months.
18. History of bleeding disorders, thrombocytopenia, hemophilia or significant anemia (hemoglobin (Hgb) < 10 gm/dl).

 neuroloop	Confidential	Protocol – The baroloop Study
--	---------------------	-------------------------------------

19. Current anticoagulation therapy (excluding antiplatelet therapy with aspirin as a sole therapy).
20. Works night shifts.
21. History of unresolved drug or alcohol use.
22. Active treatment of a psychiatric ailment.
23. Life expectancy of less than 12 months due to other disease.
24. Subject has a condition that, in the opinion of the investigator, precludes participation, including willingness to comply, with all follow-up procedures.
25. Participation in another clinical study for which follow-up is currently on-going.
26. Women who are of child-bearing age or who have the potential to become pregnant
27. Resting heart rate of <40 beats/min for patients on beta blockers or <60 beats/min for all other patients, confirmed at both baseline visits.
28. Baroreflex failure or autonomic neuropathy
29. Symptomatic, uncontrolled bradyarrhythmias
30. Atrioventricular block of any grade
31. Patients who are treated with Pacemaker and/or implantable defibrillators
32. Presence of a vagus stimulator
33. Patients who are likely to require magnetic resonance imaging (MRI) of the cervical area
34. Occupational exposure to high levels of non-ionizing radiation that may interfere with therapy
35. Patients with a limited ability to read, understand and execute adjustment procedures (for example, persons suffering from dementia).
36. Likely exposure to diathermy.

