12. Symptomatic carotid artery disease or > 70% occlusion of either carotid artery; any carotid malformation or lesion, a carotid bruit or other abnormal carotid sound.
13. Prior surgery, radiation therapy or scarring in the neck in the region of the carotid artery (e.g., patients with a tracheostomy, extensive thymectomy or thyroid surgery).
14. Limited mobility of the neck secondary to vertebral disease or prior vertebral surgery, including patients who wear a cervical support.
15. History of heart failure (NYHA class III-IV or ejection fraction < 30%), myocardial infarction, unstable angina, coronary bypass or coronary angioplasty during six (6) months prior to screening.
16. Cardiac arrhythmias (atrial fibrillation, atrial flutter, etc.) that require anticoagulation or interfere with a consistent measurement of blood pressure.
17. Syncope in the last 6 months.
18. History of bleeding disorders, thrombocytopenia, hemophilia or significant anemia (hemoglobin (Hgb) < 10 gm/dl).
19. Current anticoagulation therapy (excluding antiplatelet therapy with aspirin as a sole therapy).
20. Works night shifts.
21. History of unresolved drug or alcohol use.
22. Active treatment of a psychiatric ailment.
23. Life expectancy of less than 12 months due to other disease.
24. Subject has a condition that, in the opinion of the investigator, precludes participation, including willingness to comply, with all follow-up procedures.
25. Participation in another clinical study for which follow-up is currently on-going.
26. Women who are of child-bearing age or who have the potential to become pregnant
27. Resting heart rate of <40 beats/min for patients on beta blockers or <60 beats/min for all other patients, confirmed at both baseline visits.
28. Baroreflex failure or autonomic neuropathy
29. Symptomatic, uncontrolled bradyarrhythmias
30. Atrioventricular block of any grade

	
31. Patients who are treated with Pacemaker and/or implantable defibrillators32. Presence of a vagus stimulator33. Patients who expect to require magnetic resonance imaging (MRI) of the cervical area34. Occupational exposure to high levels of non-ionizing radiation that may interfere with therapy35. Patients with a limited ability to read, understand and execute adjustment procedures (for example, persons suffering from dementia).36. Likely exposure to diathermy.

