3.4.3. Target/intended body parts

The implantable pulse generator (IPG) is implanted subcutaneously in the left upper chest outside the rib cage, and the Lead is tunneled subcutaneously from IPG on the chest wall to the left side of the neck. The Cuff is wrapped around the left vagus nerve in the neck.

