3.6. Contraindications

Vagotomy (no usage of device after bilateral or left cervical vagotomy possible)

Diathermy – The use of shortwave diathermy, microwave diathermy, or therapeutic ultrasound diathermy on patients with an implanted VNS device is contraindicated

Baroreflex failure or autonomic neuropathy

Symptomatic, uncontrolled bradyarrhythmia's

Atrioventricular block of any grade

Patients who are treated with Pacemaker and/or implantable defibrillators

Presence of a vagus stimulator

Patients who require magnetic resonance imaging (MRI)

Occupational exposure to high levels of non-ionizing radiation that may interfere with therapy

Patients with a limited ability to read, understand and execute adjustment procedures (for example, persons suffering from dementia)

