3.7. Warnings

The warnings are also included in the manuals.

General warnings, warnings and precautions must be followed to avoid system failures.

The baroloop system is indicated only for the treatment of hypertension. Implantation for other treatments or indications has not been tested and is NOT permitted.

The baroloop system must be implanted by surgeons experienced and trained in the field of neurosurgery or in carotid sheath-related surgical procedures.

The physician who is treating the patient with baroloop system should be board-certified and have experience and expertise treating hypertension.

Patients with an implanted baroloop system should not be subjected to MRI. The baroloop system has not been tested for MRI use. Exposure to the magnetic field in an MRI might result in dislocation, heating of metallic components of the device, induced electrical currents in the Lead and/or tissue damage.

Shortwave diathermy, microwave diathermy, or therapeutic ultrasound (all of which may result in diathermy) should not be used on patients in whom the baroloop system has been implanted. Energy generated by diathermy may be transferred through implanted baroloop system and could lead to tissue or nerve damage or result in severe injury or death. Furthermore, the IPG may be damaged by the energy generated by diathermy.

Ultrasound energy may damage the Lead of the baroloop system. Therefore, physicians must avoid using ultrasound focused on regions containing implanted components of the baroloop device.

Extracorporeal lithotripsy may damage the IPG. Therefore, physicians must avoid using extracorporeal lithotripsy in the region containing the implanted IPG.

Radiation therapy may damage the baroloop system. Physicians must avoid using radiation therapy in the region of the implanted components of the baroloop system.

X-ray and CT Scans may affect the IPG, if the IPG is active and turned on. Physicians must be aware that the baroloop device must be turned off prior obtaining X-rays or CT scans in the region of the implanted components of the baroloop device.

Images obtained using X-ray and CT Scanning may be influenced by the presence of implanted components of the baroloop system when the components of the baroloop system overlay or distort the X-ray or CT scan images.

Magnetic fields may influence the function of the IPG and temporarily interrupt therapy by the baroloop system.

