4.17.3. Screening Phase

Each patient's medical records will be reviewed to assess compliance with the eligibility of the baroloop Study. Patients who are eligible based on the study enrollment criteria will proceed to the next phase of the study.

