4.21. Day of Implantation procedure

- Physical examination;
- Changes of medication regimen;
- Review and assessment of adverse events;
- Office cuff blood pressure; and
- Assessment of all Inclusion/Exclusion criteria.

4.22. baroloop System Implantation Procedure

The implantation operation should be performed as described in the baroloop Implantation Manual (BL_IM_Implantation_Manual_FIH). In brief, the procedure should be performed using a neurosurgical microscope after the initial incision in the left side of the neck is made over the location of the vagus nerve (from point 3 on). A subcutaneous pocket (size 6 x 7 cm) should be created under the skin and over the pectoralis muscle below the left clavicle to house the IPG. To access the left vagal nerve, a horizontal cervical skin incision 4-5 cm in length on the left neck should be made between the clavicle and mandible. The tissue should be carefully dissected to expose the neurovascular sheath containing the vagus. The sheath should be opened to expose the left vagus nerve over a length of approximately 3 cm. A neuroloop Cuff size should be select that matches the approximate size of the vagal nerve diameter. Before placing the Cuff, the Pill should be fixed to the underlying tissue according to the instructions in the baroloop Implantation Manual. After fixing the Pill, the Cuff should be wrapped around the vagus nerve, and proper rim alignment of the Cuff edges should be reviewed to make sure that both ends of the cuff are square and perpendicular to the long axis of the cuff. Strain relief loops in the Cable leading to the IPG should be created using the suture sleeves. The Lead should be passed subcutaneously from the cervical incision site to the pectoral pocket where the IPG is placed. The Connector should be cautiously passed through tunnelling device to the subcutaneous pectoral pocket. After removing the Tunnelling device by pulling in pectoral direction, which was inserted from the pectoral pocket to the neck, the Connector to the IPG should be cleaned, if necessary, prior to connecting it to the IPG. The Connector should be fixed in the appropriate receiving slot in the IPG using the torque key. Perform initial device testing, described below, before closing the surgical incisions.

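### Exclusion 33 screens only for cervical MRI, although the device is contraindicated in patients who require MRI with no body region stated

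*Combined protocol and SAP*

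**What the plan says.** Exclusion 33 appears twice. In Section 4.6.2 it reads "Patients who are likely to require magnetic resonance imaging (MRI) of the cervical area". In the synopsis it reads "Patients who expect to require magnetic resonance imaging (MRI) of the cervical area". The verb differs, but the limit to the neck is the same.

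The device sections are broader. The MRI entry among the contraindications in Section 3.6 reads "Patients who require magnetic resonance imaging (MRI" and ends at the closing bracket, with no region named. Section 3.7 adds "Patients with an implanted baroloop system should not be subjected to MRI" and gives the reason: "The baroloop system has not been tested for MRI use". The hazards it lists are dislocation, heating of metal parts, currents induced in the Lead, and tissue damage.

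On the position of the implant, Section 3.4.3 states: "The implantable pulse generator (IPG) is implanted subcutaneously in the left upper chest outside the rib cage". The Lead runs under the skin from there to the left side of the neck.

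Eligibility is decided on the listed criteria. Section 4.17.3 says "Patients who are eligible based on the study enrollment criteria will proceed to the next phase of the study", and the day-of-implantation list in Section 4.21 includes "Assessment of all Inclusion/Exclusion criteria". Neither section refers to Section 3.6.

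**The concern.** An eligibility list for a first-in-human implant should be at least as strict as the device's own contraindications. Here it is looser on one item. Someone known to need MRI of the lumbar spine, heart or brain meets the Section 3.6 contraindication but not exclusion 33.

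Once implanted, that patient has a problem even if nobody makes a mistake. If the site follows Section 3.7, the patient does without the MRI for as long as the device is in place. If the site does not, the patient is scanned with hardware that has not been tested for it. Section 3.2 says the implanted parts are meant to stay in, so the restriction covers the 24 months of follow-up after implantation and continues beyond them.

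**Working it through.** No arithmetic beyond counting applies. The check sets the texts side by side.

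**Step 1. Scope of each statement on MRI**

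| Place | Who or what is covered | Region |
|---|---|---|
| Section 3.6 | patients who require MRI | none stated |
| Section 3.7 | any MRI after implantation | none stated |
| Synopsis, exclusion 33 | patients expecting to need MRI | cervical only |
| Section 4.6.2, exclusion 33 | patients likely to need MRI | cervical only |

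The gap is every patient with a known need for non-cervical MRI.

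**Step 2. Is the missing region in Section 3.7 an oversight?** Probably not. In the same section, the precautions on focused ultrasound, lithotripsy, radiation therapy and X-ray or CT are each tied to the area of the implanted parts or of the pulse generator. The MRI warning is not. Reading Sections 3.6 and 3.7 as covering MRI of any region is an inference, but it is the natural one.

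**Step 3. Would a regional reading justify the cervical limit?** No. The pulse generator is in the chest and the Lead crosses from chest to neck. A limit based on where the implant lies would have to include the chest. A planned cardiac or thoracic MRI passes exclusion 33 as written.

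**Step 4. How were the other contraindications carried over?** Section 3.6 lists ten.

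| Contraindication in Section 3.6 | Exclusion | Change |
|---|---|---|
| Vagotomy | no direct counterpart (2 is close) | – |
| Diathermy | 36 | reworded, no regional limit |
| Baroreflex failure or autonomic neuropathy | 28 | none |
| Symptomatic bradyarrhythmia | 29 | apostrophe only |
| Atrioventricular block | 30 | none |
| Pacemaker or defibrillator | 31 | none |
| Vagus stimulator | 32 | none |
| MRI | 33 | limited to the cervical area |
| Non-ionizing radiation at work | 34 | none |
| Limited ability to carry out adjustments | 35 | none |

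Eight of the ten reappear in the same order as exclusions 28 to 35. Seven of the eight are unchanged apart from an apostrophe. MRI is the only one given a regional limit, and no reason is stated.

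**Step 5. Does another criterion close the gap?** No other inclusion or exclusion criterion mentions MRI, and none excludes patients who meet a Section 3.6 contraindication in general. Exclusion 24 lets the investigator reject a patient with a condition judged to preclude participation. It is a matter of opinion and does not name MRI.

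**Step 6. How long does the restriction last?** Section 4.12 gives participation of about 2 years and 2 months, that is 2 × 12 + 2 = 26 months. Follow-up after implantation is 24 of those months.

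**The case against.** The strongest reply is that Sections 3.6 and 3.7 belong to this same protocol. Section 3.13 makes the investigator responsible for using devices only as the protocol allows, and Section 3.7 requires its warnings to be followed. Section 9.8 requires familiarity with the plan, and Section 9.10 provides training against a checklist of risk mitigations. A trained investigator who knows that a patient needs MRI should stop at Section 3.6 whatever exclusion 33 says. These provisions lower the risk. None of them is an eligibility check, however, and an enrolment that satisfied exclusion 33 to the letter would look compliant when the criteria are reviewed.

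A second reply is that the patient is not strictly trapped between an unsafe scan and no imaging. Section 3.7 allows X-ray and CT, with the device off when the implant region is imaged, and the device can be removed. That is correct. CT does not replace MRI for every indication, though, and explantation is a further operation. The restriction on MRI itself still lasts as long as the device stays in.

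A third point concerns the count. Eight of ten should not suggest that two contraindications were dropped: diathermy is exclusion 36, and vagotomy is arguably covered by exclusion 2 on vagus nerve injury. Exclusion 36 was also reworded. MRI remains the only item narrowed by region.

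Finally, the study enrols at most ten subjects, the frequency of the problem is unknown, and no statistical result is affected. All of that is true and limits how much weight the point carries, but the contradiction stands.

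**Conclusion.** The concern holds. As written, the listed eligibility criteria admit patients in whom the device is contraindicated by the protocol's own Section 3.6. The conclusion rests on one reading: that an MRI contraindication with no region stated means MRI of any region. The equally unqualified warning in Section 3.7 supports it.

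The size can be stated only as a count of criteria: one of the eight contraindications carried into exclusions 28 to 35 was narrowed. How many of the up to 10 subjects might be affected cannot be estimated from the documents. This is an internal inconsistency that bears on subject safety. It touches no endpoint, sample size or analysis. It should be corrected, and other provisions in the protocol make harm less likely in the meantime.

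**What to change.** In exclusion 33, replace the limit to the cervical area with *of any body region*, in both the synopsis and Section 4.6.2. Use the likelihood wording of Section 4.6.2 in both places, so that the two lists agree and a merely hypothetical need does not exclude anyone.

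If the sponsor does mean cervical MRI only, Sections 3.6 and 3.7 have to be narrowed instead, with MRI safety data to support the change. The protocol currently says the system is untested in MRI, so that route is not open on present evidence.

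The cost is one line of wording in two places and possibly a few more screen failures, in a study that allows about 36 months to enrol up to 10 subjects.

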4.7. Informed consent

Subjects who meet the entry criteria will be asked to sign a Patient Informed Consent form as approved by the relevant regulatory authorities before any study-specific tests or procedures are performed. The Investigator or a designated member of his / her staff should approach the subject to obtain written informed consent. As far as possible, non-technical language should be used that is understandable to the subject. The background of the proposed study and the benefits and risks of the procedures and study should be explained. The subject should be provided with ample time to read the consent form and discuss it with his / her family and/or physician. The subject shall be informed that his / her participation in the clinical investigation is completely voluntary, may be withdrawn at any time without consequences, and is confidential. The Informed Consent Form must be read and understood by the subject and the subject's questions answered and must include information and a separate explicit consent regarding the patient's rights under the GDPR and/or national data protection laws or regulations. The form must be signed and dated by both the subject and Investigator. Each subject is to receive a copy of his / her signed and dated Informed Consent Form. A copy of the approved informed consent form along with a copy of each patient's signed consent form will be maintained by each Investigator in a designated clinical study administrative file.

 neuroloop	Confidential	Protocol – The baroloop Study
--	---------------------	-------------------------------------

Investigator Study personnel should explain that even if a subject agrees to participate in the study and signs the Patient Informed Consent form, the subject may not be eligible to participate if he / she fails to meet the inclusion or exclusion criteria.

Once written consent has been obtained, the subject's information will be entered on a Consent and Screening Log, which will be maintained at each site. All subjects who provide written informed consent will be entered on the log regardless of whether or not they are enrolled in the study.

As appropriate, important and new information will be provided to new and existing subjects throughout the duration of the study.

